7.1.2. Secondary Endpoints

- Pharmacokinetic analyses.
- Change (reduction) in influenza virus titer by log₁₀ tissue culture infective dose₅₀/mL (TCID₅₀/mL) and by reverse transcriptase polymerase chain reaction (RT-PCR).
- Time to alleviation of clinical symptoms of influenza (per age appropriate symptoms).
- Time to resolution of fever.
- Incidence of influenza-related complications.
- Change in viral sensitivity to the following antiviral drugs: peramivir, oseltamivir, zanamivir.

7.2. Overall Study Design and Plan

This is a multi-center, open label active-controlled study to evaluate the safety, pharmacokinetics and effectiveness of IV peramivir in children.

Up to 140 subjects will be enrolled in this study according to the following age groups:

- Birth to < 28 days: up to 10 subjects will receive IV peramivir
- 28 days < 2 years: up to 20 subjects: subjects enrolled after the approval of amendment 3 will receive IV peramivir
- 2 <4 years: up to 10 subjects: subjects enrolled after the approval of amendment 3 will receive IV peramivir
- 4 < 7 years:up to 30 subjects: subjects enrolled after the approval of amendment 3 will receive IV peramivir
- 7 < 13 years:up to 40 subjects, randomized 4:1 to IV peramivir or oral oseltamivir
- 13 < 18 years:up to 30 subjects, randomized 4:1 to IV peramivir or oral oseltamivir

Once an age cohort is filled, enrollment in that cohort will be closed and communicated with all investigators.

A subject's duration of participation in this study is expected to be 14 days.

All subjects will receive either a single dose of IV peramivir (600 mg IV for subjects \geq 13 years, 12 mg/kg IV for subjects \geq 6 months - \leq 12 years, 8 mg/kg for subjects \leq 6 months IV) or oral oseltamivir, dosed BID for 5 days.

Note, as of the date of amendment 3, no additional subjects will be randomized to receive oseltamivir.

Subjects will undergo follow-up assessments on Days 3, 7, and 14. The Day 3 visit may be a home visit (performed by a qualified study nurse). Day 7 is required to take place in the clinic, and Day 14 may either be a clinic visit, home visit, or follow-up phone call to the subject/parent/guardian.

7.3. Study Measurements and Visit Schedule

The schedule of assessments for this study is presented in Table 1.

Table 1: Study Measurements and Visit Schedule

Assessments	Screening ¹	Baseline ¹ Pre-Dose	Day 1 ¹ Post-Dose	Day 3 ²	Day 7 (+ 2 days)	Day 14 ² (+3 days)	Early Withdrawal ³
Informed Consent/Assent	X						
Inclusion/Exclusion Criteria	X						
Pregnancy Test (Urine) ⁴	X				X		X
Medical History	X						
Body Temperature ⁵	X	X	X	X	X	X	X
Physical Exam		X					
Influenza Related Complications (IRC) ⁶		X		X	X	X	X
Vital Signs ⁷		X		X	X	X	X
Concomitant Medications Review ⁸	X	X	X	X	X	X	X
Clinical Chemistries and Hematology ⁹		X			X	X ¹⁷	X ¹⁷
Urinalysis ⁹		X			X	X ¹⁷	X ¹⁷
Assessment of influenza symptoms/ activities of daily living/ eating habits 10		X	X	X	X	X	X
Subject Diary Completion/ Review ¹¹		X	X	X	X	X	X
Nasal swabs for Virology Analysis ¹²		X		X	X	X	X
Study Drug Administration ¹³		X					
Serum sample for influenza antibody analysis ¹⁴		X			X		
Pharmacokinetic (PK) Sampling ¹⁵			X				
Adverse Events			X	X	X	X ¹⁶	X ¹⁶

¹ It is expected that the date of Screening, Baseline, and Day 1 (date of study drug administration) will be the same.

² The Day 3 visit may be performed as a clinic visit or home visit (conducted by a qualified study nurse). The Day 14 visit may be performed as a home visit, clinic visit, or phone call. In the event the Day 14 assessment is a phone call the parent/ caregiver will be requested to mail the completed diary card back to the site.

³ An Early Withdrawal assessment should be conducted for subjects who withdraw before Day 7. For subjects who withdraw between Day 7 and Day 14 a telephone assessment should be completed, where possible.

⁴ Urine pregnancy test will be performed for any female post-menarche.

BioCryst Pharmaceuticals, Inc. CONFIDENTIAL

BCX1812-305

- 5 The screening temperature may be performed per the site's standard method, which will be recorded. For subsequent visits, the parent/guardian will record oral or axillary temperature with the electronic thermometer provided by BioCryst, Thereafter, the parent/caregiver will record temperature in the Subject Diary approximately every 12 hours until temperature is normal for 48 hours without antipyretic.
- 6 If an IRC is suspected, then a targeted physical examination and if needed, diagnostic testing will be conducted to record the actual presence/absence of the IRC.
- 7 Vital sign measures will include blood pressure (in children <2 only if clinically indicated), pulse rate, and respiration rate. Vital signs will be recorded at Baseline, and vital signs will be taken once on remaining study visit days.
- 8 Antipyretic medications will be recorded in the Subject Diary by the parent/caregiver daily from Day 1 through Day 14.
- 9 Clinical laboratory assessments performed at Baseline are for the purpose of establishing a baseline. Subjects may be enrolled and begin treatment with study drug prior to receiving results.
- 10 The severity of age appropriate influenza signs and symptoms will be recorded by the parent/caregiver in the Subject Diary twice daily, until all symptoms are resolved (Grade 0). Assessments of activities of daily living and eating habits will be recorded once daily until all symptoms are resolved.
- 11 On Day 1, the parents/caregivers of subjects and/or adolescent subjects are to be provided training by the study staff on completing the Subject Diary. Instructions will be reviewed with the adolescent subject or parent/caregiver at each study visit.
- 12 Swabs for virology analysis will be collected on Day 14 where possible.
- 13 Only for those subjects randomized to peramivir. The parents/caregivers of subjects randomized to the oral oseltamivir arm of the study, will record the date and time of each drug administration, from Day 1 until Day 5 (or last scheduled dose). The first dosing will be administered at the site and documented by the study staff following completion of required predose activities.
- 14 A single serum specimen will be collected, where possible, pre-dose on Day 1 and on Day 7 for analysis of influenza antibody titers. Subjects whose weight is < 10kg do not require a serum antibody sample.
- 15 Only for those subjects randomized to peramivir. A PK sample will be drawn immediately following the end of study drug infusion/administration, between 30 minutes to 1 hour post-infusion, between 1 and 3 hours post-infusion, and between 3 and 6 hours post-infusion. Note: Subjects ≥ 5 kg will have four 1.0 mL blood draws at the above stated sampling times. Subjects < 5 kg will have two 1.0 mL blood samples; one time immediately following completion of the infusion and one time between 1-3 hours post-infusion.
- 16 Any subject with unresolved moderate or severe intensity influenza symptoms or an unresolved AE and/or treatment-emergent laboratory finding that requires further medical management may be evaluated in further follow-up visits, at the Investigator's discretion.
- 17 If previous lab results are abnormal and considered clinically significant by the Investigator or significantly changed from baseline, blood specimen collection for clinical chemistry or clinical hematology tests as specified in Sections 11.2.1 and 11.2.2 may be drawn. If previous urinalysis lab results are abnormal and considered clinically significant by the Investigator or significantly changed from baseline, a urine collection for urinalysis may be completed.

8. SELECTION AND WITHDRAWAL OF SUBJECTS

8.1. Subject Inclusion Criteria

- 1. Male and non-pregnant female subjects age birth to 17 years of age.
- 2. Clinical signs and symptoms consistent with acute influenza infection consisting of an oral temperature ≥ 100°F (37.8°C) or rectal temperature ≥ 101.3°F (≥ 38.5°C) with at least one respiratory symptom (cough or rhinitis) OR a positive influenza rapid antigen test. Fever will either be documented at the time of screening or must be reported by the parent or care-giver if treatment with an antipyretic was given within 6 hours of the screening assessment. Note: enrollment at each site by clinical symptoms alone will be approved by the Sponsor at the beginning of each influenza season once influenza has been confirmed in the local community. The Sponsor may withdraw approval for symptomatic screening in any season based upon trends in influenza surveillance data. Prior to sponsor approval or after approval is withdrawn, criteria 2 must be met by a positive influenza RAT test. During the period of approval, clinical symptoms alone will be adequate to meet criteria 2.
- 3. Onset of symptoms no more than 72 hours before presentation for screening for subjects < 2 years old .
- 4. Written informed consent by parents/guardians and assent by subjects ≥ 7 years of age^{1,2}
- 5. Females who have started their menses must either be:
 - Sexually abstinent
 - Using a highly effective form of birth control such as hormone contraception (oral, patch, injection, implant or vaginal ring) or 2 barrier methods (condom with spermicide and diaphragm)

8.2. Subject Exclusion Criteria

- 1. Age > 17 years.
- 2. If less than 3 months of age at screening, history of premature birth (< 36 weeks 0 days gestation)
- 3. Weight less than 3.0 kg
- 4. Receipt of a live attenuated influenza vaccine (LAIV) within 14 days of presentation.
- 5. Females who are pregnant (positive urine or serum pregnancy test) or breast-feeding at screening.

¹ Where permitted by local IRB or state requirements.

² If age of assent is limited by local IRB or state requirements, assent must be obtained by all adolescents ≥ 14 years of age. While development varies across individual children, existing data suggest most children are capable of assent by approximately age 14. Wendler, D. S. (2006). "Assent in paediatric research: theoretical and practical considerations." J Med Ethics 32(4): 229-234.

- 6. Onset of symptoms more than 72 hours before presentation for screening for subjects < 2 years old.
- 7. Development of influenza while hospitalized for another indication.
- 8. Subjects with identified risk factors for influenza complications but with uncomplicated influenza at the time of enrollment are not excluded. This includes lung disease, heart disease, blood disorders such as sickle cell anemia, metabolic disorders and neurologic disease. In addition, mild to moderate immunocompromised status such as due to renal disease, diabetes mellitus or HIV infection with a last known CD4+ count ≥200 cells/µl are not excluded
- 9. Presence of severe immunocompromised status due to chronic disease or illness, previous organ transplant, or use of immunosuppressive medical therapy which would include oral or systemic treatment with > 10 mg prednisone or equivalent on a daily basis within 30 days of screening.
- 10. Complicated influenza characterized by any of the following:
 - a. ICU care
 - b. Evidence of organ dysfunction
 - c. Proven or suspected concomitant bacterial infection
 - d. Other known concomitant viral infection that is likely to complicate medical course such as RSV, parainfluenza virus and adenovirus. Co-infection with rhinovirus and enterovirus is allowed.

As a note, hospitalization is not an exclusion criterion when it is the usual practice of the treating institution to hospitalize children with influenza. However, the subject must have acute uncomplicated influenza.

- 11. Previous participation in Study BCX1812-305 or participation in a study of any investigational drug or device within the last 30 days.
- 12. Subjects who cannot comply with all aspects of the study protocol.

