5.4. Rationale for Study

There remains a significant unmet need for influenza therapies in children. Currently, the only available options are oral or inhalation, both of which have limitations, both in terms of administration and viral resistance. Peramivir has demonstrated efficacy and safety when used in acute uncomplicated influenza in adults. However, there is significant clinical and real world experience with pediatric use indicating that there is both efficacy and safety when used in healthy and high-risk children as young as 28 days. Most children treated to date have been Asian, so the current study will provide valuable information in other racial and ethnic groups.

Because children bear a larger burden of infection during seasonal influenza and are at greater risk for complications during pandemics, new treatments for children are needed. During the last pandemic of 2009-2010, the rates of hospitalization, admission to intensive care units, and invasive life support were higher than for past seasonal influenza with the highest proportion of seriously ill patients being children and young adults (Dominguez-Cherit, Lapinsky et al. 2009,

Jain, Kamimoto et al. 2009, WHO 2009). The approved dose of peramivir in adults is a single dose of 600 mg because of improved efficacy without an increase in safety risk. Population pharmacokinetic modeling performed by the FDA (July 2009) based on the Shionogi Studies 0816T0633 (children and adolescents) and 0722T0621 (adults) supports a target dose of 12 mg/kg/day in children (6 to 12 years) to attain exposures similar to that in adults who receive a 600 mg IV dose.

In order to provide recommendations for dosing in subjects less than 6 months of age, an updated population PK model was developed that included all available data from adult and pediatric studies, and data from an interim review of BCX1812-305. Simulations from this model indicate that a dose of 8 mg/kg/day in children from birth to < 6 months of age should provide exposure of peramivir similar to that observed in adult subjects and pediatric subjects who have completed BCX1812-305. In subjects 6 month of age and older, a 12 mg/kg dose is simulated to attain exposures in pediatric subjects similar to that in adults administered a 600 mg IV dose. Simulations indicate that in subjects < 6 months of age, the predicted exposure following an 8 mg/kg dose will not exceed that of adults.

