9. TREATMENT OF SUBJECTS

9.1. Study Drug Dose Rationale

In Study 0816T0633 conducted by Shionogi & Co. Ltd in Japan, 117 pediatric and adolescent patients with type A or type B influenza infection who were ≥ 28 days but < 16 years of age, were treated with 1 to 5 daily doses of IV peramivir in the outpatient setting. The dose of peramivir used in that study (10 mg/kg of body weight to a maximum of 600 mg) was based on pharmacokinetic modeling and target area under the plasma concentration-time curve (AUC). Peramivir, administered IV, was generally safe and well tolerated in this population. Plasma concentrations from the pediatric patients in this study were found to be within the range of plasma concentrations following administration of peramivir at 300 mg or 600 mg in adult patients with influenza, and did not exceed mean plasma concentrations following administration at 800 mg in healthy adults.

The approved dose of peramivir in adults is a single dose of 600 mg. Population pharmacokinetic modeling performed by the FDA (July 2010) based on the Shionogi Studies 0816T0633 (children and adolescents) and 0722T0621 (adults) supports a target dose of 12 mg/kg in children (≤ 12 years) to attain exposures similar to that in adults who receive a 600 mg IV dose. Children 13 and over can be treated with 600 mg/day, the adult dose. Per CDC, the average weight of a 13-year-old boy and girl are 45 kg (99 lbs) and 46 kg (101 lbs) respectively. In adult trials of peramivir in acute uncomplicated influenza, at least 30 subjects with weights between 40 kg (88 lbs) and 50 kg (110 lbs) were treated without additional risk or complication. In addition, peramivir elimination is almost exclusively renal. Renal size reaches adult at age 12 and function (i.e., glomerular filtration rate) reaches that of an adult by age 2. The population PK model built using interim PK data from BCX1812-305 included a renal maturation factor to account for the development of renal function prior to age 2. Simulations support a dose of 8 mg/kg from birth to less than 6 months of age, and 12 mg/kg in subjects 6 months of age and older. Subjects < 6 months of age are not predicted to have higher exposure of peramivir than that of adults.

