9.2. Treatments Administered

9.2.1. Peramivir

Peramivir solution for infusion is a clear, iso-osmotic, sterile, nonpyrogenic solution in 200 mg per 20 mL (10 mg/mL) single-use glass vials fitted with rubber stoppers and aluminum flip-off seals. The drug product should be stored at room temperatures up to 30°C.

Subjects < 6 months of age at time of consent will receive a single dose of IV peramivir at a dose of 8 mg/kg. Subjects ≥ 6 months $- \le 12$ years of age at time of consent will receive a single dose of IV peramivir at a dose of 12 mg/kg (up to a maximum dose of 600 mg). Subjects ≥ 13 years of age will receive a single dose of 600 mg IV peramivir administered as a short IV infusion over a minimum of 15 minutes. Peramivir must be diluted in normal saline normal saline United States Pharmacopeia (SUP).:

Because of the risk of vasovagal reactions, particularly in children with needle phobia, it is recommended that subjects be in a supine position during peramivir administration. Appropriate post infusion observation should be performed.

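### With no renal limit for entry and no renal dosing rule, a child under 7 with known moderate or worse renal impairment can be given a full dose of a renally cleared drug

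*Protocol*

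**What the plan says.** **Eligibility.** Protocol Section 8.2 item 8, repeated in the Synopsis, lists conditions that do not exclude a child, among them "mild to moderate immunocompromised status such as due to renal disease, diabetes mellitus or HIV infection". No criterion in 8.1 or 8.2 mentions creatinine, creatinine clearance or eGFR. The nearest is item 10b, "Evidence of organ dysfunction", one of the features that define complicated influenza. Item 9 removes severe immunocompromise, organ transplant and immunosuppressive therapy.

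**Dose.** In Section 9.2.1, children under 6 months "of age at time of consent will receive a single dose of IV peramivir at a dose of 8 mg/kg". From 6 months to 12 years the dose is 12 mg/kg, capped at 600 mg. There is no rule for reduced renal function.

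**Rationale.** Section 9.1 says that "peramivir elimination is almost exclusively renal". The population model it describes "included a renal maturation factor to account for the development of renal function prior to age 2"; no term for renal disease is mentioned. Section 5.4 gives the exposure aim. From 6 months, "a 12 mg/kg dose is simulated to attain exposures in pediatric subjects similar to that in adults administered a 600 mg IV dose". Below 6 months, "the predicted exposure following an 8 mg/kg dose will not exceed that of adults".

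**Timing.** Table 1 footnote 9 lets dosing start before the baseline laboratory results arrive, and Section 10.2.2.1 says those results are not needed for eligibility. Medical history is reviewed at screening (Section 10.2.1).

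**The concern.** Each of these choices is defensible alone. Together they leave a child with a known history of reduced clearance with no instruction attached. The child is not excluded, the dose formula does not see renal function, and the one measurement that would show the problem need not be back before the infusion.

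The dose was chosen to reproduce adult exposure at 600 mg, and the primary objective is safety. The protocol already lowers the dose from 12 to 8 mg/kg below 6 months, using a model that allows for immature kidneys. Reduced clearance from disease gets no comparable treatment. At stake is an avoidable exposure above the range on which the dose was justified, with two sites free to decide differently about the same child.

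**Working it through.** **Does the dose depend on weight alone?** The first two rows of Table 3 in Section 9.4.1 can be reproduced as weight x mg/kg / 10 mg/mL:
- 0 to <28 days: 3 x 8/10 = 2.4 mL and 5.5 x 8/10 = 4.4 mL.
- 28 days to <3 months: 3 x 8/10 = 2.4 mL and 7.5 x 8/10 = 6.0 mL.

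Both ranges match the table, so no renal term is hidden there. (One bound in each of the two older rows does not reproduce; that is a separate matter and is not used here.)

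**Inputs.** The plan gives no figure for exposure in renal impairment, so these are assumptions:
- f, the renal fraction of clearance: 0.8 to 1.0. Section 9.1 says almost exclusively renal but gives no number.
- k, renal function as a fraction of that expected for age: 0.75 and 0.50 as examples.
- AUC is proportional to dose.
- A child with normal function reaches the adult 600 mg AUC (Section 5.4, from 6 months).
- Upper adult reference: Section 9.1 compares pediatric concentrations with mean concentrations at 800 mg in healthy adults. Read as AUC, this is 800/600 = 1.33 times the target.

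**AUC relative to target** = 1/(1 - f(1 - k)):

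| k | f = 0.8 | f = 0.9 | f = 1.0 |
|---|---|---|---|
| 0.75 | 1/0.80 = 1.25 | 1/0.775 = 1.29 | 1/0.75 = 1.33 |
| 0.50 | 1/0.60 = 1.67 | 1/0.55 = 1.82 | 1/0.50 = 2.00 |

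At 75% function the AUC is above target but within the 800 mg reference. At half function it is above both.

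**As a dose.** The dose that would match the normal-function AUC is the planned dose x (1 - f(1 - k)). At k = 0.50 this is 12 x 0.50 to 12 x 0.60 = 6.0-7.2 mg/kg, against 12 given. Below 6 months it is 8 x 0.50 to 8 x 0.60 = 4.0-4.8 mg/kg, against 8 given.

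**Where the 800 mg reference is crossed.** Setting the ratio to R gives k = 1 - (1 - 1/R)/f. With R = 1.33, 1 - 1/R = 0.25, so k = 1 - 0.25/f: 0.69 (f = 0.8), 0.72 (f = 0.9), 0.75 (f = 1.0).

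**If normal-function AUC is below the adult target**, as it may be under 6 months, the ratios scale down:
- At 0.8 of target: 0.8 x 1.25 to 0.8 x 1.33 = 1.00-1.07 at k = 0.75, and 0.8 x 1.67 to 0.8 x 2.00 = 1.33-1.60 at k = 0.50.
- At 0.6 of target: 0.75-0.80 at k = 0.75, and 1.00-1.20 at k = 0.50.

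So in the youngest infants a mild reduction may stay at or below target, and half function may only just reach or modestly exceed it.

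**The case against.** **Existing safeguards.** Section 8.3 lets the investigator or sponsor end participation judged detrimental to the child. Screening starts at consent and includes medical history, so that power can be used before dosing. Item 10b could also be invoked. Both narrow the gap. Neither closes it: 8.3 is discretionary, 10b describes complicated influenza rather than stable chronic disease, and neither gives a cut-off. Item 8, meanwhile, points towards admission.

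**Item 8 concerns immune status, not clearance.** Renal disease can coexist with normal filtration. This stands; the point applies only where function is known to be reduced.

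**Exposure already covered in adults.** The mild case lies within the 800 mg reference, and hospitalized adults received 600 mg daily for 5 or 10 days (Section 5.3.1). This stands against any claim of harm. It does not show that the excess at moderate impairment was intended in young children.

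**Earlier trials.** A reader might infer from Section 5.3 that the need for a renal rule had already been settled. The open-label hospital trial mentions dosing adjusted for renal function, and the Japanese pediatric study excluded renal failure. But the first gave a daily regimen to acutely ill patients, where accumulation is possible, and the second shows no threshold. They are suggestive only.

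**Unseen text.** Part of the Section 5 background is not in the public text, and the abbreviation list defines renal terms that do not appear elsewhere in what is visible. The Pharmacy Manual was not seen either, though it is cited for preparation. Sections 8 and 9, where a rule would sit, are present.

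**Conclusion.** The gap is real and narrow. Following the protocol as written, a child under 7 with known renal impairment of roughly moderate degree or worse can be enrolled and given the full dose. Under the assumptions above, AUC is 1.67-2.0 times the 600 mg adult target at half of age-expected function, which also exceeds the 800 mg healthy-adult reference. At 75% function it is 1.25-1.33 times and stays within that reference. Below 6 months the ratio to adults may be lower. The result concerns AUC, not peak, and rests on the assumed renal fraction and dose-proportionality.

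Three stronger readings are tempting and not supported. The documents do not show that such a child would be harmed: no toxicity threshold is given and only one dose is planned. They do not show that any renal disease takes exposure beyond adult experience. Nor is the SAP at fault: Section 6.3.3 summarizes creatinine and laboratory toxicity shifts, so affected children could be found afterwards.

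The number affected is unknown and probably very small. Cohorts above 7 are closed, and item 9 already removes transplant recipients and severe immunocompromise. This is a cheap improvement for patient safety, of low to moderate severity.

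**What to change.** 1. Add one exclusion to Section 8.2 and the Synopsis: known renal impairment below a stated creatinine clearance or eGFR limit. About 70-75% of age-expected function keeps AUC within the 800 mg reference, depending on the renal fraction. A limit of 75% holds across the whole assumed range; 70% would allow 1/0.70 = 1.43 if clearance were wholly renal. The sponsor's own model should settle the value.
2. Make item 8 subject to that exclusion, so that renal disease above the limit stays eligible.
3. In Table 1 footnote 9, require a recent creatinine result before dosing only for children with a history of renal disease. All others are dosed as now.

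No SAP change is needed. The cost is a short amendment; creatinine is already in the Baseline panel. A few at-risk children whom item 8 now admits would be excluded, and some would be dosed later, although Section 9.4.1 asks for early treatment. Laboratory turnaround is unclear: protocol Section 11.2 implies a central laboratory for children who are not hospitalized, while the SAP Section 2.2 footnote refers to a local one. Accepting a recent existing result avoids most of the wait.
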